4.3 Analysis Sets

The following analysis sets will be defined separately for the Phase I and Phase II parts of the study (except for Safety RP2D Analysis Set which is defined across Phase I and Phase II and the Per-Protocol Set which is defined just for Phase II).

In the Phase I part of the study, HLA-A*0201-positive patients with a diagnosis of NY-ESO-1 and/or LAGE-1A positive advanced NSCLC, melanoma, urothelial carcinoma, or synovial sarcoma will be enrolled. In Phase II, HLA-A*0201 positive patients with NY-ESO-1 and/or

LAGE-1A positive advanced NSCLC, urothelial carcinoma, or synovial sarcoma will be enrolled and treated at the RP2D.

4.3.1 All Patients Set

The All Patients set includes every patient who provided their main informed consent with recorded data in the eCRF. Note that this set includes screening failures.

4.3.2 Full Analysis Set (FAS)

The FAS is a subset of the All Patients Set and it comprises all patients who received at least 1 full dose or partial dose of IMCnyeso. In Phase I, patients will be analyzed according to the planned treatment or as per the dose groups laid out in **Table 2**.

In Phase II, patients will be analyzed according to the disease cohorts laid out in **Table 3**. The FAS will be used for all listings of raw data, demography and baseline characteristics, and all analyses unless specified otherwise.

4.3.3 Safety Analysis Set (SAF)

The SAF is a subset of All Patients Set and it comprises all patients who received at least 1 full dose or partial dose of IMCnyeso. Patients will be classified in this set according to initial treatment received (see **Table 2**) or disease cohort in Phase II (**Table 3**). The SAF will be used for the safety summary of the study. In Phase I, the SAF will be equivalent to FAS if received doses are equal to planned doses (or sufficiently close to be in the same dose grouping).

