Figure 6-2: Schematic Illustration of a 2-Step IPE Regimen

Rules for the 2-step IPE regimen are as follows:

- The initial target dose level must be a permitted escalation step based on BLRM output and the consensus of the SST
- The initial target dose level must not exceed the 1-step dose-escalation MTD (if established)
- The C1D8 dose level must be at least one dose level below the initial target dose, and must be a dose level that has been evaluated in ≥ 3 patients using a fixed-dose or 1-step IPE regimen, with a decision to escalate based on the BLRM output and SST review of all available relevant data
- Escalation of the target dose in subsequent cohorts may proceed as in the main and 1-step dose escalation:
 - Separate MTD/RP2D may be identified using fixed-dose, 1-step IPE, and 2-step IPE regimens
 - DLT will be attributed to the dose level of the most recently administered dose prior to onset of the DLT (eg, a DLT with onset on C1D4 would be attributed to the C1D1 dose level, while a DLT with onset on C1D10 would be associated to the C1D8 dose level)
- The dose levels for C1D1 and C1D8 remain fixed for all subsequent cohorts
- Patients receiving 2-step IPE must receive the C1D1 and C1D8 doses prior to receiving the target dose
- If a 2-step IPE regimen is evaluated in Phase I, it may be selected for further evaluation in Phase II

An example of how IPE might be implemented is shown in [Figure 6-3](#).

[figure not shown]

Figure 6-3: Representative Escalation Path Incorporating IPE

IPE = intra-patient escalation.

Actual dose levels will be determined using BLRM and must be approved by SST. In this scenario, after 3 patients were enrolled in Cohort 4 and completed DLT evaluation, the recommended next dose per BLRM was 195 mcg. The SST determined that the 195 mcg dose would be better tolerated using a 2-step escalation regimen, and so Cohort 5 was opened with a dose of 30 mcg on C1D1, 100 mcg on C1D8, and 195 mcg as the target dose (weekly starting on C1D15).

In addition, a patient who is enrolled in a lower dose cohort may move to a higher dose cohort once all the following criteria are met:

- The patient has completed at least 3 cycles of treatment
- The patient did not experience any DLT or any \geq Grade 3 treatment-related toxicity
- The patient does not have any ongoing \geq Grade 2 treatment-related toxicity
- The higher dose cohort has completed SST review with a decision to escalate or was determined to be the MTD/RP2D

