6.11 Definition of Maximum Tolerated Dose and Recommended Phase II Dose

The MTD will be determined if the following conditions are met:

1. At least 6 patients have been treated at this dose and associated treatment regimen (ie, fixed-dose, 1-step IPE, or 2-step IPE).
2. The dose has the highest posterior probability that the true DLT rate is in the target interval for toxicity (16%–33%), as predicted by the BLRM. The interval boundaries of 16% and 33% are chosen to be consistent with the traditional 3+3 design toxicity boundary (ie, 1/6 and 1/3).
3. The dose satisfies the EWOC principle (the probability that the DLT rate lies within the excessive toxicity or the unacceptable toxicity window is less than 25%).

The RP2D will be defined as the dose and associated treatment regimen selected for further evaluation in Phase II by the SST. The RP2D will be determined from a synthesis of all data available, including safety, tolerability, PK, pharmacodynamics, and preliminary anti-tumor activity observations from Phase I. The RP2D must not exceed the MTD as determined by the BLRM. A minimum of 6 patients will be treated at the RP2D in Phase I and monitored through the DLT evaluation period before enrollment in Phase II may begin.

During Phase II, following enrollment of at least 12 subjects, if the observed rate of Grade 3 and/or Grade 4 toxicity considered related to IMCnyeso and meeting the definition of DLT is > 30%, a safety teleconference will be convened with the SST to determine if the cohorts should continue enrollment.

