3.4 Dose Adjustment/Modifications

All doses administered to subsequent cohorts of patients will be determined by the SST and will be guided by the BLRM and will be subject to both the EWOC principle and the escalation rule. Dose-escalation decisions will be made by the SST, which will consist of the Study Investigators, the Sponsor Medical Monitor, and a Statistician. For each cohort, dose escalation or de-escalation decisions will be based on the SST's review of all relevant data available, from all dose levels evaluated in the ongoing study, including safety information, DLTs, all \geq Grade 2 toxicity data, PK, and pharmacodynamic data from evaluable patients (as defined in Section 6.10.2 of protocol version 4.0). The data and BLRM dose recommendations will be discussed and agreed upon during the dose-escalation teleconference (DETC), and all decisions will be documented in the meeting minutes and shared with all participating Principal Investigators.

The actual dose levels that have been tested in this study are shown in **Table 1** below. Actual doses will be determined using the BLRM and must be agreed upon by the SST.

Table 1 - IMCnyeso Dose Levels for Phase I Dose Escalation

Cohort number	Cohort description	IMCnyeso Dose(s) Tested	Enrollment (n)
1	3 mcg fixed dose	3 mcg	4
2	10 mcg fixed dose	10 mcg	3
3	30 mcg fixed dose	30 mcg	5
4	100 mcg fixed dose	100 mcg	3
5	30-100 mcg intra-patient dose escalation	30-100 mcg	5
6	30-100-180 mcg intra-patient dose escalation	30-100-180 mcg	4
7	30-100-300 mcg intra-patient dose escalation	30-100-300 mcg	6 (planned)

To better understand the safety, tolerability, and PK profile of single agent IMCnyeso, additional cohorts of patients may be enrolled at preceding dose levels or intermediate dose levels, before or in parallel, while proceeding with further dose escalation. The outcome from these cohorts will be included in the BLRM.

If the first 2 patients in a previously untested dose level experience a DLT, additional enrollment in that cohort will stop, the BLRM will be updated with this new information, and the SST will evaluate the available safety, PK, and pharmacodynamic data. By incorporating information gained at the preceding dose levels and provided the BLRM predicts that the risk of excessive toxicity remains below 25% (EWOC), additional patients may be enrolled at this dose level or a lower dose level as agreed upon by the SST.

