4.2.1 Treatment and Disease Groups for Reporting

The Phase I safety data will be listed, summarized, and analyzed overall and by dose group where dose groups may incorporate pooling of dose levels; the exact extent of pooling will be defined after Phase I actual doses administered are known, and is expected to use the Recommended Phase 2 dose (RP2D) as threshold (see **Table 2**).

Patients who enroll in multiple cohorts will be represented once for each cohort and once in the total/overall study columns for summaries that are based on baseline data (e.g. demographics, medical history). Listing will be presented for patients who are escalated to a higher dose.

Table 2 – Potential Phase I Dose Groups

Treatment Group	Dose Group (Label for TLF Reporting)*	Patients included
IMCnyeso < x mcg QW	< RP2D	All Phase I dose escalation cohorts receiving a dose less than RP2D
IMCnyeso = x mcg QW	= RP2D	All Phase I dose escalation cohorts receiving the same dose as RP2D
IMCnyeso > x mcg QW	> RP2D	All Phase I dose escalation cohorts receiving a dose greater than RP2D

* x mcg is the Recommended Phase 2 Dose (RP2D) where x is determined during Phase I and administered IV over 1-2 hours.

In Phase II, patients will be analyzed according to the disease cohorts laid out in **Table 3**.

Table 3 - Phase II Disease Cohorts at RP2D

Cohort	Disease Cohort
Cohort 1	Advanced NSCLC
Cohort 2	Urothelial Cancer
Cohort 3	Synovial Sarcoma

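### Phase I safety tables sort patients by one mcg threshold, which pools fixed-dose with intra-patient-escalation patients although the RP2D is a dose plus a regimen

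*SAP*

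**What the plan says.** **Classification.** SAP 4.3.3 states for the safety set: "Patients will be classified in this set according to initial treatment received". For Phase I it points to Table 2. Protocol 9.2.2 has the same rule and does not mention IPE.

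**Groups.** Table 2 (SAP 4.2.1) has three rows: below, equal to and above the RP2D. They are described in terms such as "All Phase I dose escalation cohorts receiving a dose less than RP2D" and "All Phase I dose escalation cohorts receiving the same dose as RP2D". The footnote makes the threshold a single number: "x mcg is the Recommended Phase 2 Dose (RP2D) where x is determined during Phase I". The table is labelled as potential, and the SAP adds that "the exact extent of pooling will be defined after Phase I actual doses administered are known".

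**Use.** The DLT table (SAP 8.1) and the TEAE summaries (SAP 8.2) both take their groups from SAP 4.2.1.

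**RP2D.** Protocol 6.11: "The RP2D will be defined as the dose and associated treatment regimen selected for further evaluation in Phase II by the SST". Protocol 6.10.1: "Separate MTD/RP2D may be identified using fixed-dose, 1-step IPE, and 2-step IPE regimens".

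**Cohorts.** SAP Table 1 (SAP 3.4) lists four fixed-dose cohorts and three IPE cohorts, the last being "30-100-300 mcg intra-patient dose escalation".

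**Pooled RP2D set.** SAP 4.3.4 admits any patient from either phase with one complete dose at the RP2D level. Regimen is not a condition.

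**The concern.** Protocol 6.10.1 introduces IPE because stepped dosing is expected to reduce cytokine-mediated events, with two steps possibly doing more than one. Regimen is therefore a factor that the trial itself expects to change tolerability. Table 2 has no place for it, and the SAP does not say which dose of a stepped sequence decides a patient's row.

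DLT incidence and the frequency and severity of AEs are primary Phase I endpoints (SAP 3.2.1). A column that mixes fixed-dose and IPE patients reports an average over regimens that the protocol keeps apart. A reader of the study report could not tell whether a rate belongs to the dose or to the way it was reached.

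Two related gaps follow from the same wording. A patient who moves to a higher cohort under Protocol 6.10.1 remains classified by the initial treatment, so later AEs are counted at the lower dose. The Safety RP2D set can also include patients who met the RP2D level only as an intermediate step.

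**Working it through.** **Inputs (SAP Table 1).** Fixed dose: 3 mcg n = 4, 10 mcg n = 3, 30 mcg n = 5, 100 mcg n = 3. One-step IPE: 30-100 mcg n = 5. Two-step IPE: 30-100-180 mcg n = 4, and 30-100-300 mcg n = 6 (planned).

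**Check of inputs.** Fixed: 4 + 3 + 5 + 3 = 15, which agrees with the 15 treated patients in Protocol 1.4. IPE: 5 + 4 + 6 = 15. Total: 30.

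**Rule applied.** The documents do not state the RP2D, so levels of 30, 100, 180 and 300 mcg are assumed in turn. Each cohort is placed by its final target dose, as fixed + IPE:

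| Assumed RP2D level | < RP2D | = RP2D | > RP2D | IPE patients sharing a column with fixed-dose patients |
|---|---|---|---|---|
| 30 mcg | 7 + 0 | 5 + 0 | 3 + 15 | 15 of 15 |
| 100 mcg | 12 + 0 | 3 + 5 | 0 + 10 | 5 of 15 |
| 180 mcg | 15 + 5 | 0 + 4 | 0 + 6 | 5 of 15 |
| 300 mcg | 15 + 9 | 0 + 6 | 0 + 0 | 9 of 15 |

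At least one column is mixed at each level. The RP2D column itself is mixed only at 100 mcg.

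**Weight of IPE in the mixed column.** The pooled event rate is (n_fixed × rate_fixed + n_IPE × rate_IPE) / (n_fixed + n_IPE). The IPE weight is 5/8 = 62.5% at 100 mcg, 5/20 = 25% at 180 mcg and 9/24 = 37.5% at 300 mcg. At 30 mcg it is 15/18 = 83%.

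**Safety RP2D set.** Count the Phase I patients whose planned sequence contains the level. At 100 mcg: 3 fixed + 5 from 30-100 + 4 + 6 who pass through 100 mcg as the intermediate step = 18 at most. Only 5 of the 18 had the 30-100 regimen. At 180 mcg the count is 4 and at 300 mcg it is 6, each from a single regimen.

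**Moves to a higher cohort.** Protocol 6.10.1 allows a move after three completed cycles, so AEs after the move fall outside the 28-day DLT period. They are still treatment-emergent under SAP 8.2. SAP 4.2.1 says how to count multi-cohort patients only for baseline summaries, and adds a listing of escalated patients. No rule moves their later AEs out of the initial group. The documents do not give the number of such patients, so this part cannot be sized.

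**The case against.** **Table 2 is not final.** This stands. It is labelled as potential and the pooling is to be settled later. SAP 4.3.2 also lets the full analysis set be shown by planned treatment. The point is therefore about a default that needs correcting, not about a fixed grouping. But cohorts 5 to 7 are already in the SAP, the expected threshold is still the RP2D in mcg, and in an open-label study later pooling is chosen with safety data in view.

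**A reader might infer that every IPE patient is reported in the 30 mcg group**, because all three IPE cohorts start at 30 mcg. That would give a group of 5 + 15 = 20 and, with an RP2D of 180 or 300 mcg, an empty '= RP2D' row. The documents do not support this reading:
- SAP 4.3.3 says that the safety set matches the full analysis set when received doses equal planned doses. That would fail for IPE patients grouped by first dose.
- Table 2 allocates cohorts, not a patient's first infusion.
- SAP 8.6 treats 30/100/300 as the assignment.

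The word 'initial' is more naturally read as the first assigned cohort.

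**A reader might also infer that the RP2D decision lacks regimen-level safety.** It does not rest on Table 2, which cannot be filled in until the RP2D is known. The decision comes from Study Safety Team review and the BLRM. DLTs are attributed to the most recent dose (Protocol 6.10.1), and an MTD needs at least six patients at that dose and regimen (Protocol 6.11). Protocol 13.3.1 provides for a separate model for target doses after IPE.

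**Some detail is available elsewhere.** DLTs and AEs are listed by patient and PK is by cohort. This limits the harm, but listings do not replace the summary of a primary endpoint.

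**Conclusion.** The point holds for reporting. Followed as written, a threshold in mcg alone pools fixed-dose with IPE patients in at least one Phase I safety column at each RP2D level tried. The mix is 3 + 5 in '= RP2D' at 100 mcg, 15 + 5 in '< RP2D' at 180 mcg and 15 + 9 in '< RP2D' at 300 mcg. At 180 or 300 mcg the '= RP2D' column is clean and only the comparison column is affected. These counts assume that the target dose governs the row, that cohort 7 enrols its planned six patients, and that Table 2 keeps its present form.

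The 'initial treatment' rule also keeps post-move AEs in the lower-dose group, and the Safety RP2D set disregards regimen. The latter matters most at 100 mcg, where up to 18 patients qualify and 5 had the 30-100 regimen.

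Dose-escalation decisions and the choice of RP2D are not affected, and no hypothesis test depends on the grouping. This is a cheap improvement to the DLT and safety tables.

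**What to change.** In the SAP, before the pooling is settled:

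1. State in 4.3.3 that initial treatment means the first assigned cohort and regimen.
2. Redefine the Phase I safety groups in 4.2.1 by regimen (fixed, one-step IPE, two-step IPE) and target dose. On the present cohorts this gives fixed 3/10/30/100 mcg with n = 4/3/5/3, one-step 30-100 with n = 5, and two-step 30-100-180 and 30-100-300 with n = 4 and 6 (planned).
3. Do not pool across regimen types. If a pooled column is wanted, print the by-cohort columns beside it.
4. Define the Safety RP2D set in 4.3.4 by regimen as well as dose.
5. Tabulate AEs that start after a move to a higher cohort separately from those before it.

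The cost is SAP wording and table headings. The drawback is columns of 3 to 6 patients, so the percentages will be coarse: one event in 3 patients is 33%. No change to dosing or trial conduct is involved.

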7.2.2 Treatment Compliance and Modifications

Study treatment will be administered to the patient at the study site by trained study staff. Patients compliance with the prescribed regimen will be assured as all administrations will be performed by site staff under the supervision of the study investigator or his/her designee. Therefore, no analysis of compliance is planned. However, dose interruptions and reductions may occur (see Section 8.6).

8 Safety Analysis

Safety analysis will be conducted on the SAF for the Phase I dose escalation and separately for the Phase II expansion cohorts. Combined outputs for safety may be produced based on the Safety RP2D Analysis Set.

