8.2 Adverse Events

All AEs regardless of study drug relationship will either be collected from the signing of consent up to the end of the 30 day follow-up based on current protocol versions 3.0 and 4.0 or 90 day follow up based on the previous protocol versions. Those AEs with onset 31-90 days after the last dose will be flagged in the separate adverse events listing.

- 1) Treatment-emergent adverse events (TEAEs) are defined as any adverse event after the first dose of study drug within 30 days of the last dose of study drug or prior to subsequent anti-cancer therapy, whichever is sooner. For adverse events on C1D1, the event onset time relative to the first dose time will be considered (if relative or actual times are available), otherwise AE starting on C1D1 will be assumed treatment-emergent.

The AE summary tables include only AEs that are new or worsened during the on-treatment period (TEAEs). However, all safety data (including those from the pre- and post-treatment periods) will be listed and those collected during the pre-treatment and post-treatment period are to be flagged.

The incidence of TEAEs will be summarized by system organ class (SOC) and/or PT, severity (based on NCI CTCAE v.4.03 grades), and relation to study treatment by treatment group (as defined in Section 4.2.1). Serious TEAEs resulting in death and non-fatal serious TEAEs will be listed by patient and tabulated by treatment group. There will be a separate listing for TEAE leading to treatment discontinuation.

AEs will be coded by MedDRA version 20.0.

For the purpose of inclusion in TEAE tables, incomplete AE onset and end dates will be imputed as follows:

- Missing onset dates (where UK and UKN indicate unknown or missing day and month respectively):
 - UK-MMM-YYYY: If the month and year are different from the month and year of the first dose of study drug, assume 01-MMM-YYYY. If the month and year are the same as the first dose of study drug month and year, and the end date (after any imputation) is on or after the first dose of study drug, then assume the date of the first dose of study drug. If the month and year are the same as the first dose of study drug month, and year and the end date (after any imputation) is prior to the first dose of study drug, then assume the end date for the onset date.

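### Phase I safety tables hold each patient in the initial dose group, so events that start after a move to a higher-dose cohort are counted under the lower dose

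*SAP*

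**What the plan says.** - **Grouping.** SAP 4.3.3 states: "Patients will be classified in this set according to initial treatment received". Protocol 9.2.2 has the same rule.
- **Moves between cohorts.** Protocol 6.10.1 provides that "a patient who is enrolled in a lower dose cohort may move to a higher dose cohort once all the following criteria are met". The criteria include "The patient has completed at least 3 cycles of treatment" and "The patient did not experience any DLT". They also rule out patients with a related toxicity of Grade 3 or higher, or an ongoing related toxicity of Grade 2 or higher. The higher cohort must already have passed safety review.
- **Population for the tables.** The opening of SAP Section 8 says "Safety analysis will be conducted on the SAF for the Phase I dose escalation". SAP 8.2.1 takes percentages out of that set, by the groups of SAP 4.2.1.
- **Event window.** SAP 8.2 defines a treatment-emergent event as "any adverse event after the first dose of study drug within 30 days of the last dose of study drug", cut short only by subsequent anti-cancer therapy. SAP 8.3 takes the worst laboratory grade as the maximum after baseline. SAP 8.5 tabulates the worst on-treatment QTcF.
- **Patients in more than one cohort.** SAP 4.2.1: "Patients who enroll in multiple cohorts will be represented once for each cohort", and once in the total. The same sentence limits this to summaries built on baseline data. The section adds a listing of escalated patients.

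**The concern.** Each rule is reasonable alone; together they misplace events. A mover's window stays open through the whole period on the higher dose, while the column label stays at the starting dose. The lower-dose column then collects events from two dose levels over a longer period. The higher-dose column receives neither the event nor the patient.

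The affected tables report Phase I primary endpoints: incidence and severity of AEs and SAEs, and changes in laboratory values, vital signs and ECGs (SAP 3.2.1). The usual direction of the error is to make the lower dose look more toxic than it is, and so to flatten the apparent dose gradient in the study report.

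**Working it through.** The documents give no figure that depends on this rule, so there is none to reproduce. The check follows one patient through the rules and then sizes the effect from the cohort sizes.

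**1. One patient, followed through.** Suppose a patient starts in the 10 mcg cohort, completes three 28-day cycles (3 × 28 = 84 days), moves to a higher-dose cohort and has a first Grade 3 event there.
- Safety set group: 10 mcg, the initial treatment.
- Treatment-emergent: yes, because the event falls before 30 days after the last dose.
- Column: the 10 mcg cohort, or the pooled group containing it.
- An event type already reported before the move adds nothing to incidence, but a worse episode raises the maximum grade in the lower-dose column.

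**2. Does another rule re-assign the event?**
- The once-per-cohort rule in SAP 4.2.1 covers baseline summaries only. A mover can therefore count in two cohort columns for demographics and in one for adverse events.
- The listing of escalated patients (SAP 4.2.1) and the counts of escalations (SAP 8.6) show that a move occurred. They do not re-attribute events.
- The Safety RP2D set (SAP 4.3.4) takes in anyone with a full dose at the RP2D. It is summarised by disease, its outputs are optional (SAP Section 8), and it does not say whether events before the move are left out.

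None of these assigns an adverse event to the dose at onset.

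**3. Where the error shows.** SAP Table 2 proposes pooled groups below, at and above the RP2D. A move that stays below the RP2D does not change group, so nothing is misplaced in those tables. The error appears when the move crosses the threshold, and in any display by individual cohort.

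**4. Size without assumed event rates.** SAP Table 1 gives cohort sizes of 4, 3, 5, 3, 5, 4 and 6 (the last planned). One mover whose first event of a given type comes after the move shifts the incidence by 100/n points.

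| Group | n | Shift per mover |
|---|---|---|
| Smallest cohort | 3 | 100/3 = 33.3 points |
| Largest cohort | 6 | 100/6 = 16.7 points |
| Below RP2D, if cohort 4 is the RP2D | 4+3+5 = 12 | 100/12 = 8.3 points |
| Below RP2D, if cohort 7 is the RP2D | 4+3+5+3+5+4 = 24 | 100/24 = 4.2 points |

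The cohort of 6 is the highest in Table 1, so a patient could leave it upward only if a higher cohort opened. For cohorts 1 to 6 the range is 33.3 to 20 points (n = 3 to 5).

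**5. Illustration with assumed rates.** Let pL and pH be the true incidences at the lower and higher dose, N the size of the lower group and m the number of movers, all crossing the boundary. The column reads

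[(N − m) × pL + m × (1 − (1 − pL)(1 − pH))] / N.

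| pL, pH | N | m = 1 | m = 3 | True difference | Apparent difference, m = 1 to 3 |
|---|---|---|---|---|---|
| 5%, 25% | 4 | 10.9% | 22.8% | 20 points | 14.1 to 2.2 |
| 5%, 25% | 24 | 6.0% | 8.0% | 20 points | 19.0 to 17.0 |
| 10%, 40% | 4 | 19.0% | 37.0% | 30 points | 21 to 3 |
| 10%, 40% | 24 | 11.5% | 14.5% | 30 points | 28.5 to 25.5 |

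The values of pL, pH and m are assumptions; the documents give none of them. With m = 0 the column reads pL exactly. Movers are selected for tolerance, so pH may overstate their own risk, and these shifts may be too large.

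**The case against.** The strongest reply is that the tables do not drive the dose decision. A reader might infer that the MTD or RP2D is chosen on misattributed toxicity. The documents do not support that:
- Escalation uses the dose-determining set by actual dose received (SAP 4.3.6).
- The intra-patient escalation rules charge a DLT to the dose most recently given (protocol 6.10.1).
- The DLT window is 28 days (protocol 6.10.2), while a move needs at least 84.
- The Phase I summary report is cut after the MTD/RP2D is determined (SAP Section 1).

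One narrow gap remains: a late event that the Study Safety Team chooses to call a DLT (protocol 6.12) would enter the by-group DLT table of SAP 8.1.

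A reader might also infer that a formal comparison between doses is biased. SAP Section 4 plans no hypothesis tests, so the tables are descriptive. Nor is toxicity at the RP2D necessarily lost from the report, since a patient who moves to the RP2D enters the Safety RP2D set. It would also be wrong to assume that movers spend at least half their time on the higher dose. Three cycles is a minimum: a patient who moves after six and stays three more spends 3/9, one third.

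Finally, grouping by initial treatment has a merit. It keeps patients selected for good tolerance out of the higher-dose denominator. That stands, and the remedy should preserve it. It does not justify leaving the lower-dose window open after the move.

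**Conclusion.** The point holds as a reporting defect. As written, the SAP counts events that start after a move in the initial dose group, and no other provision corrects this; the listing, the escalation counts and the Safety RP2D set help only in part. The consequence is a distorted descriptive picture of safety by dose for Phase I primary endpoints. It is confined to displays by cohort and, with Table 2 pooling, to moves across the RP2D threshold. The dose decision is essentially untouched.

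The per-patient shifts in step 4 rest only on the Table 1 sizes and on which cohort becomes the RP2D. The total effect depends on the number of movers and may be nil. The change is still worth making, because groups this small can be altered visibly by one patient and the correction is cheap.

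**What to change.** In SAP 4.3.3 and Section 8:
- End the initial group's safety window at the first dose in the higher-dose cohort. Apply this to adverse events, SAEs, worst laboratory, vital-sign and ECG values, and dose modifications.
- Report later-onset events in a separate column, such as *after move to higher dose*, labelled with the dose received. Count each patient once in the total.
- Keep movers out of the higher-dose group's own denominator, because they were selected for tolerance.
- In SAP 4.3.4, state whether events before the move are excluded from the Safety RP2D set.

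The cost is one derived date, obtainable from the exposure data, and one extra table column. No new data are needed, and dosing and patient management do not change. The downside is a shorter observation window for movers in their initial group; showing exposure time for each column would make that visible.
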